### **8.1. Subject Inclusion Criteria**

To be eligible for study participation, all subjects must meet all the following inclusion criteria:

1. Age 18 to 80 years, inclusive
2. Has experienced self-reported daily or near-daily moderate to severe pruritus before Screening
3. Has a mean daily WI-NRS score indicative of moderate to severe pruritus (score  $\geq 4$ ) during Screening (Day -7 through Day -1); data from at least 4 of the 7 days are required to be considered an acceptable profile
4. If currently taking medications to treat the cholestatic disorder (including obeticholic acid [OCA]), must be on a stable dose for >12 weeks before Screening and plans to maintain the regimen throughout the study
5. If currently taking a fibrate, must be on a stable dose for >12 weeks before Screening and plans to maintain the regimen throughout the study
6. Either is not treated with or has been on a stable regimen with any medications to treat pruritus for >4 weeks before Screening and plans to maintain the regimen throughout the study
7. If female, must have a negative serum pregnancy test at Screening and be willing to not donate eggs from Screening until after the last dose of study drug and:
  - a. Is surgically sterile; or
  - b. Has been amenorrhoeic for  $\geq 1$  year without an alternative medical cause; or
  - c. If of childbearing potential, must agree to use at least 1 form of an acceptable method of contraception from Screening until the last dose of study drug. Acceptable birth control methods include:

---

 Women of childbearing potential are defined as those who are fertile, following menarche and until becoming postmenopausal unless permanently sterile. Permanent sterilization methods include hysterectomy, bilateral salpingectomy, and bilateral oophorectomy. A postmenopausal state is defined as no menses for 12 months without an alternative medical cause.

- Barrier methods of contraception (eg, male condom, female condom, cervical cap or diaphragm, and contraceptive sponge)
  - Combined (estrogen and progestogen containing) hormonal contraception associated with inhibition of ovulation
  - Progestogen only hormonal contraception
  - Intrauterine device
  - Intrauterine hormone releasing system
  - Bilateral tubal occlusion
  - Vasectomized partner

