10. History of recurrent bacterial cholangitis or recent episode within 3 months before Screening
11. Endoscopic interventions with therapeutic intent such as biliary duct dilation within 3 months before Screening or planned during the study
12. History of significant small bowel resection or short bowel syndrome
13. Presence of a concomitant disease or a history of any medical condition that, in the opinion of the Investigator, could pose undue risk to the subject, impede completion of the study procedures, or would compromise the validity of the study measurements
14. Clinically relevant medical history, physical examination, vital sign, standard 12-lead electrocardiogram (ECG), chemistry, hematology, urinalysis, or coagulation results at Screening beyond what is expected for subjects with a cholestatic disorder that would place the subject at undue risk as deemed by the Investigator
15. Has any of the following laboratory results at Screening:
  - a. Total bilirubin >2.0 mg/dL; total bilirubin >2.0 mg/dL is acceptable for subjects with medically documented Gilbert's syndrome if direct bilirubin is <0.3 mg/dL
  - b. Alanine aminotransferase (ALT) or aspartate aminotransferase (AST) >5× ULN
  - c. ALP >10× ULN
  - d. International normalized ratio (INR) >1.3
  - e. Platelet count <150,000/μL
  - f. Urine albumin to creatinine ratio ≥30 mg/g
16. Estimated glomerular filtration rate <60 mL/min/1.73 m^2 as determined by the Chronic Kidney Disease Epidemiology Collaboration equation at Screening
17. History of human immunodeficiency virus (HIV) or positive for HIV infection at Screening
18. Significant history of abuse of drugs, solvents, or moderate alcohol consumption (≥1 serving or unit/day on average for women and ≥2 servings or units/day on average for men; 1 unit = 12 ounces [350 mL] of 5% alcohol beer, 5 ounces [150 mL] of 12% wine, or 1.5 ounces [45 mL] of 80 proof distilled spirits) in the past 2 years before Screening
19. Has received a prohibited medication within 2 weeks or 5 half-lives of Day 1, whichever is longer, as described in [Section 8.4.1](#)
20. Participation in any clinical study with an investigational or approved drug/device within 30 days before Screening or is planning to participate in another clinical study with an investigational or approved drug/device while enrolled in this study
21. History of known or suspected hypersensitivity to any component of the study drug

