#### **8.4.1. Prohibited Concomitant Medications**

Subjects taking immunosuppressant/immunomodulating agents may not receive live, attenuated vaccines during participation in this study. Medications with known nephrotoxic potential (eg, aminoglycosides, contrast dye, bisphosphonates, and nonsteroidal anti-inflammatory drugs) are prohibited from use during the study [REDACTED]

[REDACTED] Table 3 lists examples of excluded medications that are substrates for BCRP, OAT1, CYP2B6, or CYP2C8, or inhibitors of OAT3. If a subject receives a prohibited concomitant medication during the study, the Investigator, in consultation with the Medical Monitor, may interrupt or discontinue study drug as warranted for reasons of protecting subject safety.

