		
medications that are dependent on BCRP, OAT1, CYP2B6, or CYP2C8 for elimination should be carefully considered. Additionally, concomitant medications that are substrates for BCRP, OAT1, CYP2B6, or CYP2C8 should be monitored appropriately, and those with a narrow therapeutic window should have the timing of administration considered or the medication substituted if its use is prohibited in this study; concomitant medications that are inhibitors of OAT3 should be thoughtfully weighed for use with EP547 (Section 8.4.1).
 

 
Notably, no adverse changes in serum chemistry markers (eg, creatinine and blood urea nitrogen [BUN]) were observed with daily doses of EP547 as high as 225 mg for 1 week in healthy volunteers in the Phase 1 study. Nonetheless, out of precaution, subjects participating in this study are required to have an estimated glomerular filtration rate <math>\geq 60</math> mL/min/1.73 m^2 as determined by the Chronic Kidney Disease Epidemiology Collaboration equation at Screening, and medications with known nephrotoxic potential are prohibited from use during the study (Section 8.4.1). Additionally, any clinically meaningful new, worsening from baseline, or abnormal laboratory findings or symptoms suggestive of acute kidney injury (AKI) (eg, 'blood urea increased' or
	

Section	Amendment 2.0	Amendment 3.0	Reason for Change

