8.4.1. Prohibited Concomitant Medications	
Subjects taking immunosuppressant/immunomodulating agents may not receive live, attenuated vaccines during participation in this study. Medications with known nephrotoxic potential (eg, aminoglycosides, contrast dye, bisphosphonates, and nonsteroidal anti-inflammatory drugs) are prohibited from use during the study as are some medications that are substrates for BCRP, OAT1, CYP2B6, or CYP2C8. Table 3 lists examples of excluded medications that are substrates for BCRP, OAT1, CYP2B6 or CYP2C8.
 
Table 3: Examples of Excluded Medications that are Substrates for BCRP, OAT1, CYP2B6, or CYP2C8
	
Subjects taking immunosuppressant/immunomodulating agents may not receive live, attenuated vaccines during participation in this study. Medications with known nephrotoxic potential (eg, aminoglycosides, contrast dye, bisphosphonates, and nonsteroidal anti-inflammatory drugs) are prohibited from use during the study as are some medications that are [REDACTED]
 
[REDACTED]
 
[REDACTED]
 
Added fibrates (eg, gemfibrozil), immunomodulators (eg, teriflumomide), and uricosurics (eg, probenecid) as examples of OAT3 inhibitors to Table 3.
	
Updated to reflect the results from a recently completed nonclinical study suggesting that inhibition of OAT3 could increase exposure of EP3583.

9.4.1.1. Visit 1 (Day -28 to Day -1)	
<del>▲ SARS-CoV-2 RT-PCR test</del>
	
Deleted text
	
Testing for SARS-CoV-2 was removed given recent advancements in the prevention and treatment of the virus.

12.11 SARS-CoV-2 Testing (Deleted heading in Amendment 3.0)	
<del>12.11 SARS-CoV-2 Testing</del>  <del>Subjects will be tested for SARS-CoV-2 (COVID-19) at Screening via RT-PCR test. A positive test result for COVID-19 will exclude the subject from enrolling in the study, even if the subject is asymptomatic, regardless of vaccination status.</del>
	
Deleted text
	
Testing for SARS-CoV-2 was removed given recent advancements in the prevention and treatment of the virus.

Section	Amendment 2.0	Amendment 3.0	Reason for Change

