# 4.2 Analysis Sets

The analysis sets are defined as follows for the Double-Blind Treatment Period:

• Full Analysis Set: All subjects who are randomized and take at least 1 dose of randomized study drug will be included in the Full Analysis Set. Subjects in the Full Analysis Set will be analyzed according to randomized treatment assignment. If a subject is incorrectly stratified (i.e., randomized according to an incorrect stratification), the subject will be analyzed under the randomized treatment for the stratum recorded in the IWRS. All efficacy and PD analyses will be based on the Full Analysis Set.

- Per Protocol Set: The Per Protocol Set is a subset of the Full Analysis Set containing subjects who meet study eligibility requirements and have no protocol deviations that might impact the assessment of efficacy measurements. Subjects will be analyzed according to randomized treatment assignment. The Per Protocol Set will be used for sensitivity analyses relating to efficacy and PD. Protocol deviations that qualify for exclusion from the Per Protocol Set include:
  - Deviations of inclusion/exclusion criteria
  - Non-permitted concomitant medications that may meaningfully impact efficacy outcomes (e.g., receipt of prohibited and/or a rescue medication qualifying as an intercurrent event)
  - Meaningful dosing and/or randomization error(s)
  - Any other important protocol deviation deemed by the Sponsor to warrant exclusion from the Per Protocol set

Any protocol deviations that govern exclusion from the Per Protocol Set will be determined prior to database lock and primary analysis.

- Safety Analysis Set: All subjects who are randomized and take at least 1 dose of randomized study drug will be included in the Safety Analysis Set. Safety analyses will be based upon treatment actually received.
- PK Set: All subjects who receive at least 1 dose of EP547 and provide adequate blood samples for bioanalysis will be included in the PK Set.

Data summaries to be presented on both the Safety Analysis Set and the Full Analysis Set will only be produced on both analysis sets if there is a difference in the population groups.

An Open-Label Extension Analysis Set will be determined as all subjects who complete the Double-Blind Treatment Period and receive at least one dose of study drug in the Open-Label Extension Period and will be used to summarize all available data collected in both the Double-Blind and Open-Label Extension Periods.

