# 4.4.5 Exploratory Endpoint Analysis Methods

# 4.4.6 Sensitivity Analysis of Efficacy Endpoints

Sensitivity analyses of the primary endpoint will be conducted to better assess the impact of intercurrent events on the efficacy conclusions. The intercurrent events of interest include receipt of prohibited and/or rescue medications while on study and early withdrawal of study drug. The treatment policy strategy will be used for the primary estimand.

The while on treatment strategy will be used as a sensitivity analysis to further explore the intercurrent event of prohibited and/or rescue medication usage. The difference in means between treatment groups in the weekly WI-NRS score at the last visit prior to receipt of prohibited and/or rescue medications (or the last derived weekly WI-NRS score, for those who never require prohibited and/or rescue medication) will be presented during the Double-Blind Treatment Period. For those subjects that receive a prohibited and/or rescue medication, any WI-NRS scores reported after the receipt of medication will be excluded from the analysis.

Determination of intercurrent events based on use of a prohibited and/or rescue medication will be based on review of the Concomitant Medication eCRF. Before study unblinding, the sponsor will review all reported concomitant medications, including onstudy changes to background medications, to determine which qualify as an intercurrent event for prohibited or rescue medication usage. This external assessment will be documented in the study files and integrated into the sensitivity analysis.

The analysis of the primary efficacy endpoint will be analyzed for the Full Analysis Set using multiple imputations (MI) assuming data missing at Week 6 to be missing at random (MAR) (Section 4.4.7.2), and for the Per Protocol Set using observed data.

Treatment group comparisons will use the methodology described in Section 4.4.3 for sensitivity analysis of the primary endpoint.

Secondary and PD endpoint analyses during the Double-Blind Treatment Period will be repeated for the Per Protocol Set as supportive analyses.

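### Inclusion 5 accepts stable use of any fibrate, but exclusion 19 removes users of any fibrate covered by Table 3, so each fibrate needs one status throughout

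*Protocol*

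**What the plan says.** Four places in the protocol bear on a patient who takes a fibrate.

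- **Section 8.1, inclusion 5** (repeated in the synopsis): "If currently taking a fibrate, must be on a stable dose for >12 weeks before Screening and plans to maintain the regimen" for the whole of the study. It sets no limit on the agent and does not refer to Section 8.4.1.
- **Section 8.4.1**: Table 3 "lists examples of excluded medications that are substrates for BCRP, OAT1, CYP2B6, or CYP2C8, or inhibitors of OAT3". The table itself is not in the public text. The Amendment 3.0 summary in Appendix I records what was done to it: "Added fibrates (eg, gemfibrozil), immunomodulators (eg, teriflumomide), and uricosurics (eg, probenecid) as examples of OAT3 inhibitors to Table 3". The reason given is a nonclinical result suggesting that OAT3 inhibition could raise exposure to EP3583, a code that the visible text does not explain.
- **Section 8.2, exclusion 19**, which points to Section 8.4.1: "Has received a prohibited medication within 2 weeks or 5 half-lives of Day 1, whichever is longer".
- **Section 5.5.2**, as given in the Amendment 3.0 summary: "concomitant medications that are inhibitors of OAT3 should be thoughtfully weighed for use with EP547", again with a pointer to Section 8.4.1.

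The SAP repeats the prohibition in 3.3.2, but says that only some of the substrates and OAT3 inhibitors are barred. SAP 4.2 removes subjects from the Per Protocol Set for eligibility deviations and for non-permitted medication that could meaningfully affect efficacy. SAP 4.4.6 says, for subjects who receive a prohibited or rescue drug, that "any WI-NRS scores reported after the receipt of medication will be excluded from the analysis" in the while-on-treatment sensitivity analysis. It leaves the decision on which drugs count to a sponsor review before unblinding.

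**The concern.** Inclusion 5 treats fibrates as acceptable background treatment that has to continue. The Table 3 entry treats at least one of them as an excluded drug. The Amendment 3.0 summary shows changes to several eligibility criteria (contraception, UDCA, bilirubin, eGFR) but none to inclusion 5, so the Table 3 change may not have been carried through.

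Two things are at stake. The first is conduct: sites may treat the same patient differently. One site enrols on inclusion 5 a patient taking a drug that was listed because of a possible rise in exposure. Another screens the patient out under exclusion 19. An enrolled subject could then have study drug interrupted under Section 8.4.1 for taking the very drug that inclusion 5 told the subject to continue. The second is analysis: the subject would already be on a listed drug before the first post-baseline score, and the SAP has no stated rule for background medication that was accepted at entry and never changed.

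**Working it through.** No figure in the plan depends on this point, so the check sets the rules side by side.

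**Is the Table 3 entry current?** The protocol history lists Amendment 3.0 as the latest version. The summary is used here only for what that version added. The current Section 8.4.1 carries the matching OAT3 wording, so the entry is not superseded text.

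**Do the time windows overlap?** Inclusion 5 needs a stable dose for more than 12 weeks before Screening, and a plan to continue. Exclusion 19 looks back at least 2 weeks (14 days) from Day 1, or longer if 5 half-lives is longer. A patient who continues as inclusion 5 requires has been taking the drug through the whole of those 14 days. The overlap is complete.

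**Cases:**

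1. *The fibrate is not covered by Table 3.* Exclusion 19 does not apply through Table 3. Inclusion 5 works as a stability rule and there is no conflict.
2. *The fibrate is covered by Table 3 and the patient continues it.* Inclusion 5 is met and exclusion 19 is also met. The patient is removed.
3. *The fibrate is covered by Table 3 and the patient stops to clear the window.* Exclusion 19 is avoided, but the plan to maintain the regimen is broken if the patient counts as a current user. Section 8.3 also asks subjects to keep prescribed medication unchanged from Screening unless the Medical Monitor is consulted.

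For a Table 3 fibrate, then, inclusion 5 describes a patient who cannot properly be enrolled. If Table 3 covers the whole class, inclusion 5 has no current fibrate user left to apply to. No visible passage exempts stable users.

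**What follows in the analysis if such a patient is enrolled?**

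- *Primary analysis:* the Full Analysis Set takes everyone randomised who had at least one dose, and the treatment-policy strategy keeps data after prohibited medication (protocol 14.2, SAP 4.4.3). The subject's data are used as planned.
- *Per Protocol Set:* an exclusion 19 breach is an eligibility deviation. That ground for removal stands apart from the medication ground, which is limited to drugs that could meaningfully affect efficacy. Deviations that exclude a subject are settled before database lock.
- *While-on-treatment sensitivity analysis:* receipt predates Day 1. If the drug were classed as an intercurrent event, the subject's post-baseline scores would fall after receipt. Whether it is so classed depends on the sponsor's review.

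**How many subjects?** The count is 58 times the share on a Table 3 fibrate. The documents give neither that share nor the list of agents, so no count follows.

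**The case against.** The strongest reply is that the rules can be applied together. Protocol 9.4.1.1 requires all inclusion criteria and no exclusion criterion to be met, and lets eligibility questions go to the Medical Monitor. Inclusion 5 is conditional: it demands stability and does not override an exclusion. On this reading, users of a listed fibrate are excluded and users of any other must be stable. This stands. A reader might infer that the same patient is both eligible and ineligible. Strictly, exclusion 19 decides.

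The scope is also uncertain. Table 3 is not visible, Section 8.4.1 is redacted near the statement of scope, and SAP 3.3.2 bars only some of these drugs. The Table 3 entries pair a class label with an example. Section 8.4.1 also gives a vaccine rule for subjects on immunomodulating agents, another class with a Table 3 entry, so a class label may not ban the whole class. A class-wide conflict is therefore the literal reading but is not established. By the same logic, the Section 5.5.2 wording may concern only drugs that are not prohibited. It is softer than Section 8.4.1 and should be aligned with it, but it is not clearly a separate contrary rule.

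Three further inferences go too far:

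- *A count of subjects.* An assumed fibrate share of 5% to 20% would give 58 × 0.05 = 2.9 to 58 × 0.20 = 11.6, or about 3 to 12. The share is not in the documents, and the sum treats every fibrate as prohibited.
- *Loss of all six weekly scores.* That is a worst case under SAP 4.4.6. The review before unblinding covers all concomitant medications and decides which qualify.
- *A link to the kidney events of special interest.* The visible text gives EP3583 exposure as the reason for the change and does not connect OAT3 inhibition to those events.

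What remains is that inclusion 5 neither limits the agent nor points to Table 3, so a site can follow it and enrol a patient on a listed drug.

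**Conclusion.** The inconsistency is real in the current protocol, but narrow. It holds for any fibrate covered by Table 3. Gemfibrozil is the firm case, and the rest of the class follows only on the literal wording of an entry known from the amendment summary. Its direct effect is an avoidable eligibility deviation and uneven handling across sites.

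The primary analysis is not affected. Any effect on results is confined to the Per Protocol Set and the while-on-treatment sensitivity analysis, and depends on the sponsor's classification before lock or unblinding. The number of affected subjects is unknown. The conclusion assumes that the unseen Table 3 and the redacted text contain no exemption for stable users. If they do, inclusion 5 still needs to point to it.

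**What to change.** In the protocol, reconcile inclusion 5 (synopsis and 8.1), exclusion 19, Section 8.4.1 with Table 3, and the Section 5.5.2 wording, so that each fibrate has one status in all of them. Have inclusion 5 cross-refer to Table 3. If only some fibrates are barred, name them in both places. Which fibrates are allowed is for the sponsor's clinical and pharmacology teams, and this point takes no position on it.

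In SAP 4.2 and 4.4.6, add a sentence that background medication permitted at entry and continued unchanged is not a prohibited-medication intercurrent event. That gives the sponsor's review a stated rule for these subjects.

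The cost is one protocol clarification and one SAP sentence. Depending on the sponsor's choice, some fibrate users become screen failures and others become clearly eligible.

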## 8.2. Subject Exclusion Criteria

All subjects meeting any of the following criteria will be excluded from this study:

1. Pruritus is attributed mainly to any disease unrelated to PBC or PSC
2. Prior liver transplant or presently listed for transplantation
3. Is receiving ongoing ultraviolet B (UVB) treatment or plasmapheresis or anticipates receiving such treatments during the study
4. Evidence of compensated or decompensated cirrhosis based on ANY of the following:
  - a. Historical liver biopsy demonstrating cirrhosis
  - b. Liver stiffness as assessed by a FibroScan® score of  $\geq 16.9$  kPa for subjects with PBC or  $\geq 14.4$  kPa for subjects with PSC within 6 months of Screening
  - c. History or presence of portal hypertension with complications, including known gastric or esophageal varices, ascites, spontaneous bacterial peritonitis, hepatic encephalopathy, history of variceal bleeds, or related therapeutic or prophylactic interventions (eg, non-selective beta blockers being used to prevent complications of portal hypertension [propranolol, nadolol, or carvedilol], insertion of variceal bands, transjugular intrahepatic portosystemic shunt, or direct intrahepatic portocaval shunt)
5. History of malignancy of any organ system, including but not limited to hepatocellular carcinoma, cholangiocarcinoma, and gall bladder carcinoma, treated or untreated, within the past 5 years (localized squamous cell or basal cell carcinoma of the skin that have been excised or resolved is not exclusionary)
6. Alternate causes of liver diseases such as hepatic sarcoidosis, alcoholic liver disease, histology confirmed autoimmune hepatitis, overlap hepatitis, or nonalcoholic steatohepatitis (NASH), or uncontrolled viral hepatitis as defined in [Section 12.9](#)
7. Presence of documented secondary sclerosing cholangitis (eg, ischemic cholangitis, recurrent pancreatitis, intraductal stone disease, severe bacterial cholangitis, surgical or blunt abdominal trauma, recurrent pyogenic cholangitis, choledocholithiasis, toxic sclerosing cholangitis due to chemical agents, or any other cause of secondary sclerosing cholangitis) on prior clinical investigations

8. Immunoglobulin G4 (IgG4) >4× upper limit of normal (ULN) at Screening or evidence of systemic IgG4-related disease
9. Current evidence of clinically significant high-grade strictures or presence of biliary stent at Screening
10. History of recurrent bacterial cholangitis or recent episode within 3 months before Screening
11. Endoscopic interventions with therapeutic intent such as biliary duct dilation within 3 months before Screening or planned during the study
12. History of significant small bowel resection or short bowel syndrome
13. Presence of a concomitant disease or a history of any medical condition that, in the opinion of the Investigator, could pose undue risk to the subject, impede completion of the study procedures, or would compromise the validity of the study measurements
14. Clinically relevant medical history, physical examination, vital sign, standard 12-lead electrocardiogram (ECG), chemistry, hematology, urinalysis, or coagulation results at Screening beyond what is expected for subjects with a cholestatic disorder that would place the subject at undue risk as deemed by the Investigator
15. Has any of the following laboratory results at Screening:
  - a. Total bilirubin >2.0 mg/dL; total bilirubin >2.0 mg/dL is acceptable for subjects with medically documented Gilbert's syndrome if direct bilirubin is <0.3 mg/dL
  - b. Alanine aminotransferase (ALT) or aspartate aminotransferase (AST) >5× ULN
  - c. ALP >10× ULN
  - d. International normalized ratio (INR) >1.3
  - e. Platelet count <150,000/μL
  - f. Urine albumin to creatinine ratio ≥30 mg/g
16. Estimated glomerular filtration rate <60 mL/min/1.73 m^2 as determined by the Chronic Kidney Disease Epidemiology Collaboration equation at Screening
17. History of human immunodeficiency virus (HIV) or positive for HIV infection at Screening
18. Significant history of abuse of drugs, solvents, or moderate alcohol consumption (≥1 serving or unit/day on average for women and ≥2 servings or units/day on average for men; 1 unit = 12 ounces [350 mL] of 5% alcohol beer, 5 ounces [150 mL] of 12% wine, or 1.5 ounces [45 mL] of 80 proof distilled spirits) in the past 2 years before Screening
19. Has received a prohibited medication within 2 weeks or 5 half-lives of Day 1, whichever is longer, as described in [Section 8.4.1](#)
20. Participation in any clinical study with an investigational or approved drug/device within 30 days before Screening or is planning to participate in another clinical study with an investigational or approved drug/device while enrolled in this study
21. History of known or suspected hypersensitivity to any component of the study drug

22. Female who is pregnant, nursing, or intends to become pregnant during the study
23. Is directly affiliated with the study at the study site or is an immediate family member (spouse, parent, child, or sibling; biological or legally adopted) of personnel directly affiliated with the study at the study site
24. Is employed by Escient Pharmaceuticals, Inc., (that is an employee, temporary contract worker, or designee responsible for the conduct of the study) or is an immediate family member of an employee of Escient Pharmaceuticals, Inc.
25. Subject is, in the opinion of the Investigator, not suitable to participate in the study

